4.5.3.5. Vital Signs

The following summaries will be provided for vital signs data:

- Summary of Changes in Heart Rate from Baseline
- Summary of Increases in Blood Pressure from Baseline

- Summary of Changes in Temperature from Baseline

The oncology standard categories for Heart Rate in bpm is:

- Heart Rate in bpm: ‘Decrease to <60’, ‘Increase to >100’

The oncology standard categories for Systolic Blood Pressure in mmHg are:

- ‘Any Grade Increase’
- ‘Increase to Grade 2 (140-159)’
- ‘Increase to Grade 3 (≥ 160)’

Note: ‘Any Grade Increase’ will be footnoted as Grade 0 (<120), Grade 1 (120-139), Grade 2 (140-159), Grade 3 (≥ 160).

The oncology standard categories for Diastolic Blood Pressure in mmHg are:

- ‘Any Grade Increase’
- ‘Increase to Grade 2 (90-99)’
- ‘Increase to Grade 3 (≥ 100)’

Note: ‘Any Grade Increase’ will be footnoted as Grade 0 (<80), Grade 1 (80-89), Grade 2 (90-99), Grade 3 (≥ 100).

The oncology standard category ‘Decrease to < 90’ will be used for the Summary of decreases in Systolic Blood Pressure from Baseline.

The oncology standard categories of clinical concern for Temperature are:

4.6. Other Analyses

Performance Status

ECOG performance status will be summarized at baseline and each post-baseline scheduled visit. Summaries will use frequency and percentage of subjects at each planned assessment time.

4.6.1. Subgroup analyses

No subgroup analysis is planned in this study.

4.7. Interim Analyses

No interim analysis is planned in part 1.

4.8. Changes to Protocol Defined Analyses

Changes from the originally planned statistical analysis specified in the protocol are detailed in [Table 1](#).

Table 1 Changes to Protocol Defined Analysis Plan

Protocol Defined Analysis	SAP Defined Analysis	Rationale for Changes

Analysis and reporting of part 2 of the study	
No part 2 analysis is described	
The study is getting terminated in part 1

5. SAMPLE SIZE DETERMINATION

Part 1:

A maximum of 15 participants will be enrolled to each scheduled dose level of ipilimumab in Part 1.

6. SUPPORTING DOCUMENTATION

6.1. Appendix 1 Study Population Analyses

The study population analyses will be based on the Safety, unless otherwise specified.

Study population analyses including analyses of subject's disposition, protocol deviations, demographic and baseline characteristics, past and current medical conditions, prior and concomitant medications, disease characteristics at initial diagnosis and at screening, will be based on GSK Core and Oncology Data Standards.

6.1.1. Participant Disposition

A summary of the number of subjects in each of the analysis sets described in Section 3 will be provided. Number of subjects based on the Safety will be summarized by country and site for each dose level.

A summary of subject status and reason for study withdrawal will be provided. This display will show the number and percentage of subjects who have completed the study or have withdrawn from the study, including primary and secondary (if any) reasons for study withdrawal. Reasons for study withdrawal will be presented in the order they are displayed in the eCRF (Electronic Case Report Form). Subjects who die for any reason during on-treatment period will be considered to have completed the study.

A summary of study treatment status will be provided. This display will show the number and percentage of subjects who discontinued study treatment and a summary of the primary reasons for discontinuation of study treatment. Reasons for study treatment discontinuation will be presented in the order they are displayed in the eCRF.

A listing of treatment discontinuation will be generated. The listing will include last dose date and primary reasons for study treatment discontinuation.

The number of subjects will be summarized by Country, Site ID and Investigator ID. This summary must be produced based on the safety population. The total column, summarizing subjects regardless of treatment, should always be included. Rows should be sorted alphabetically by country, then in numerical order by Site ID

6.1.2. Demographic and Baseline Characteristics

The demographic characteristics (e.g., age, race, ethnicity, sex, height, and baseline body weight) will be listed and summarized. Age, height and weight will be summarized using the mean, standard deviation, minimum, median, and maximum. In addition, age will also be categorized and summarized by 18-64, 65-74, 75-84, and ≥ 85 . The count and percentage will be computed for race, ethnicity and sex.

A separate summary of age ranges based on the ITT population will be provided. Age will be summarized in categories: 18-64, 65-84, and ≥ 85 . Race and racial combinations will also be summarized. Listing of Race will also be provided.

6.1.3. Protocol Deviations

Important and non-important protocol deviations (including deviations related to study inclusion/exclusion criteria, conduct of the trial, patient management or patient assessment) will be summarised and important protocol deviations will be listed.

Protocol deviations will be tracked by the study team throughout the conduct of the study in accordance with the Protocol Deviation Management Plan.

- Data will be reviewed prior to freezing the database to ensure all important deviations are captured and categorised on the protocol deviations dataset.
- This dataset will be the basis for the summaries and listings of protocol deviations.

A separate listing of all inclusion/exclusion criteria deviations will also be provided. This summary will be based on data as recorded on the inclusion/exclusion page of the eCRF.

6.1.4. Prior and Concomitant Medications

Prior medications will be coded using GSK Drug coding dictionary and summarized. The summary of prior medications will show the number and percentage of subjects taking prior medications by Ingredient.

Concomitant medications will be coded using GSK Drug coding dictionary and summarized. The summary of concomitant medications will show the number and percentage of subjects taking concomitant medications by Ingredient. Multi-ingredient products will be summarized by their separate ingredients rather than as a combination of ingredients.

In the summary of concomitant medications, each subject is counted once within each unique ingredient. For example, if a subject takes Amoxicillin on two separate occasions, the subject is counted only once under the ingredient “Amoxycillin”. In the summary of concomitant medications, the ingredients will be summarized by the base only, using CMBASECD and CMBASE.

Concomitant medications will be summarized separately for medications with onset date within the on-therapy period and for medications with onset date within the pre-therapy period. Note: In order to be considered a concomitant medication, the concomitant medication must have been taken at some point during the on-therapy window.

6.1.5. Prior Medical Condition and Disease Characteristics

Disease history and characteristics (primary tumor type, lesion status, time since initial diagnosis, stage at initial diagnosis, time since last progression) will be summarized. Indicators (yes/no) for the following, collected at screening, will also be summarized: measurable disease, non-target lesions, and metastatic disease. Medical conditions present at screening will be listed and will be summarized by past and current. Disease

history and characteristics, as well as these medical conditions, will be presented in data listings.

A summary of disease burden at baseline will be provided. Information on sites of metastatic disease at screening will be summarized.

Prior cancer related surgeries will be summarized and listed.

6.2. Appendix 2 Data Derivations Rule

6.2.1. Criteria for Potential Clinical Importance

To identify values of potential clinical importance, National Cancer Institute Common Terminology Criteria for Adverse Events (NCI-CTCAE v [5.0]) will be used to assign grades for laboratory parameters including clinical chemistry, hematology, liver function tests, QTc (Fridericia's) values, LVEF and vital signs (heart rate, blood pressure, temperature).

Reference ranges for all laboratory parameters collected throughout the study are provided by the laboratory. A laboratory value that is outside the reference range is considered either high abnormal (value above the upper limit of the reference range) or low abnormal (value below the lower limit of the reference range). Note: a high abnormal or low abnormal laboratory value is not necessarily of clinical concern. The laboratory reference ranges will be provided on the listings of laboratory data. Clinical laboratory test results outside of the reference range will be flagged in the listings.

6.2.2. Study Period

6.2.2.1. Study Phases

Adverse events, serious adverse events, death and other safety domains will be assigned to the study phases defined below. Partial dates will be imputed into full dates, if applicable, for slotting data to the appropriate categories below. Flag variables (time in relation to study phase) indicating the study time periods will be added to the ADaM variable APHASE, and the treatment emergent AE flag will be created to ADAAE variable TRTEMFL.

Assessments and events will be classified according to the time of occurrence relative to Study Treatment Start Date.

Study Phase	Definition
Pre-Treatment	Date < Study Treatment Start Date
On-Treatment	Study Treatment Start Date \leq Date \leq Study Treatment Stop Date + 30 days
Post-Treatment	Date > Study Treatment Stop Date + 30 days

For parameters where time is not collected, Day 1 assessments are assumed to be taken prior to first dose and used as baseline.

Study Phase	Definition
Pre-Treatment	Date < Study Treatment Start Date
On-Treatment	Study Treatment Start Date \leq Date \leq Study Treatment Stop Date
Post-Treatment	Date > Study Treatment Stop Date

6.2.2.2. Study Phases for Concomitant Medication

Study Phase	Definition
Prior	If medication end date is not missing and is before 28 days prior to study treatment start date
Concomitant	Any medication that is not a prior

NOTES:

- Please refer to Section 6.2.6.: Reporting Standards for Missing Data for handling of missing and partial dates for concomitant medication. Use the rules in this table if concomitant medication date is completely missing.

6.2.2.3. Treatment Emergent Flag for Adverse Events

Flag	Definition
Treatment Emergent	
Non-serious AEs
 
In general, all AEs with a start date after treatment are considered emergent regardless of AE start date is before or after treatment stop date.
 
 • If AE onset date is on or after treatment start date & on or before treatment stop date + 30 days 
 ◦ Study Treatment Start Date \leq AE Start Date \leq Study Treatment Stop Date + 30 days ◦ AE Start Date is missing 
Serious AE/AESI
 
 ◦ If AE onset date is on or after treatment start date & on or before treatment stop date + 30 days Study Treatment Start Date \leq AE Start Date \leq Study Treatment Stop Date + 30 days ◦ AE Start Date is missing 
Missing AE Start Date will be imputed following rules in Section 12.7.2.1 for determining Treatment Emergent AEs.

NOTES:

- [If the study treatment stop date is missing, then the AE will be considered to be On-Treatment.]
- If the study treatment stop date is missing, then the AE will be On-Treatment.
- Time of study treatment dosing and start/[stop] time of AEs should be considered, if collected.

6.2.3. Study Day and Reference Dates

Study Day for Safety

 • Calculated as the number of days from First Dose Date: 
 ◦ Ref Date = Missing \rightarrow Study Day = Missing ◦ Ref Date $<$ First Dose Date \rightarrow Study Day = Ref Date – First Dose Date ◦ Ref Date \geq First Dose Date \rightarrow Study Day = Ref Date – (First Dose Date) + 1
Study Day for ITT

 • Calculated as the number of days from Randomization Date: 
 ◦ Ref Date = Missing \rightarrow Study Day = Missing ◦ Ref Date $<$ Randomization Date \rightarrow Study Day = Ref Date – Randomization Date ◦ Ref Date \geq Randomization Date \rightarrow Study Day = Ref Date – Randomization Date + 1

6.2.4. Assessment Window

The visit assigned to the assessment as entered in the CRF (nominal visit) will be used for reporting.

6.2.5. Multiple measurements at One Analysis Time Point

Mean of the measurements will be calculated and used in any derivation of summary statistics but if listed, all data will be presented.

If there are two values within a time window, the value closest to the target day for that window will be used. If values are the same distance from the target, then the mean will be taken.

Participants having both High and Low values for Normal Ranges at any post-baseline visit for safety parameters will be counted in both the High and Low categories of “Any visit post-baseline” row of related summary tables. This will also be applicable to relevant Potential Clinical Importance summary tables.

6.2.6. Handling of Partial Dates

Element	Reporting Detail		
General	
 Partial dates will be displayed as captured in participant listing displays. However, where necessary, display macros may impute dates as temporary variables for sorting data in listings only. Imputed partial dates will not be used to derive study day, time to onset or duration (e.g., time to onset or duration of adverse events), or elapsed time variables (e.g., time since diagnosis). In addition, imputed dates are not used for deriving the last contact date in overall survival analysis dataset. 		
Adverse Events	
 Imputations in the adverse events dataset are used for slotting events to the appropriate study time periods and for sorting in data listings. Partial dates for AE recorded in the CRF will be imputed using the following conventions: 
 
 Missing start day	 
 If study treatment start date is missing (i.e. participant did not start study treatment), then set start date = 1st of month. Else if study treatment start date is not missing: 
 If month and year of start date = month and year of study treatment start date, then 
 If stop date contains a full date and stop date is earlier than study treatment start date, then set start date= 1st of month. 	
 
 	Missing start day	
 If study treatment start date is missing (i.e. participant did not start study treatment), then set start date = 1st of month. Else if study treatment start date is not missing: 
 If month and year of start date = month and year of study treatment start date, then 
 If stop date contains a full date and stop date is earlier than study treatment start date, then set start date= 1st of month.
Missing start day	
 If study treatment start date is missing (i.e. participant did not start study treatment), then set start date = 1st of month. Else if study treatment start date is not missing: 
 If month and year of start date = month and year of study treatment start date, then 
 If stop date contains a full date and stop date is earlier than study treatment start date, then set start date= 1st of month. 		

Element	Reporting Detail	
	Missing start day and month	
 ▪ Else set start date = study treatment start date. 
 ○ Else set start date = 1st of month. • If study treatment start date is missing (i.e. participant did not start study treatment), then set start date = January 1. • Else if study treatment start date is not missing: 
 ○ If year of start date = year of study treatment start date, then 
 ▪ If stop date contains a full date and stop date is earlier than study treatment start date, then set start date = January 1. ▪ Else set start date = study treatment start date. ○ Else set start date = January 1.
	Missing stop day	Last day of the month will be used.
	Missing stop day and month	No Imputation
	Completely missing start/end date	No imputation
Concomitant Medications/ Blood Supportive Products		
 • Partial dates for any concomitant medications recorded in the CRF will be imputed using the following convention:
	Missing start day	
 • If study treatment start date is missing (i.e. participant did not start study treatment), then set start date = 1st of month. • Else if study treatment start date is not missing: 
 ○ If month and year of start date = month and year of study treatment start date, then 
 ▪ If stop date contains a full date and stop date is earlier than study treatment start date, then set start date= 1st of month. ▪ Else set start date = study treatment start date. ○ Else set start date = 1st of month.
	Missing start day and month	
 • If study treatment start date is missing (i.e. participant did not start study treatment), then set start date = January 1. • Else if study treatment start date is not missing:

Element	Reporting Detail	
		
 ○ If year of start date = year of study treatment start date, then 
 ▪ If stop date contains a full date and stop date is earlier than study treatment start date, then set start date = January 1. ▪ Else set start date = study treatment start date. • Else set start date = January 1.
	Missing end day	A '28/29/30/31' will be used for the day (dependent on the month and year)
	Missing end day and month	A '31' will be used for the day and 'Dec' will be used for the month.
	Completely missing start/end date	No imputation
New Anti-Cancer Therapy/ Radiotherapy/ Surgical Procedures for Efficacy Evaluation (e.g., response rate, time to event)		
 • Completely missing start dates will remain missing, with no imputation applied; • Partial start dates will be imputed using the following convention: 
 • If both month and day are missing, no imputation will be applied; • If only day is missing: 
 ○ If the month of partial date is the same as the month of last dosing date, minimum of (last dosing date + 1, last day of the month) will be used for the day; ○ If the month of partial date is the same as the month of last disease assessment and the last disease assessment is PD, minimum of (last date of disease assessment + 1, last day of the month) will be used for the day; ○ If both conditions above are met, the later date will be used for the day; ○ Otherwise, a '01' will be used for the day; • Completely or partial missing end dates will remain missing, with no imputation applied;
ECG		
 • Missing baseline values are assumed to have baseline value <450 for QTc

Trademarks

Trademarks of the GlaxoSmithKline Group of Companies	Trademarks not owned by the GlaxoSmithKline Group of Companies
NONE	SAS WinNonLin

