4.3.1.1. Definition of Overall Response Rate (ORR) and Disease Control Rate (DCR)

ORR is defined as the percentage of participants with a best overall confirmed Complete Response (CR) or Partial Response (PR) at any time as per RECIST1.1

DCR is defined as the percentage of participants with best overall confirmed complete response, partial response or stable disease at any time as per RECIST1.1

Best overall response (BOR) will be derived on investigator assessments of overall response at each visit recorded from the start of treatment until the criteria for progression are met (considering any requirement for confirmation when needed), or the date of initiation of new anti-cancer therapy (Note: This excludes palliative radiotherapy), or death date, whichever is earliest, as assessed by the investigator per RECIST 1.1.

For RECIST 1.1,

To be assigned a status of confirmed CR/PR, a confirmatory disease assessment should be performed no less than 4 weeks (28 days) after the criteria for response are first met.

Responses of CR/PR that do not meet the requirements of confirmed CR/PR are still eligible to be considered SD if it has met the SD criteria.

For RECIST 1.1, to be assigned a status of SD, follow-up disease assessment(s) must have met the SD criteria at least once after the first dose at a minimum of 8 weeks (56 days) from baseline. If the minimum of 8 weeks (56 days) for SD is not met, the best overall response will depend on the subsequent assessments. For example, if an

assessment of PD follows the assessment of SD and SD does not meet the minimum 8-week requirement the best response will be PD. Alternatively, subjects lost to follow-up after an SD assessment not meeting the minimum time criteria will be considered not evaluable.

If NE (Not Evaluable) is recorded in between initial and confirmatory CR or PR then it can be disregarded to obtain the Best Response

A SD in between an initial PR and confirmation PR can also be disregarded to obtain the Best Response of PR (see below table)

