4.3.1.2. Main analytical approach

ORR

The number and percentage of participants with the BOR in the following response categories will be summarized: CR, PR, iCR, iPR. The corresponding exact 95% CI for ORR and iORR will also be provided. Participants with unknown or missing responses will be treated as non-responders, i.e., these participants will be included in the denominator when calculating percentages of response. A figure displaying maximum reduction in tumor size and listing of subject level responses will be generated.

DCR

The number and percentage of participants with the BOR in the following response categories will be summarized: CR, PR, SD, iCR, iPR, iSD. The corresponding exact 95% CI for DCR and iDCR will also be provided. Participants with unknown or missing responses will be treated as non-responders, i.e., these participants will be included in the denominator when calculating percentages of response.

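### Best overall response is cut off at the start of new anti-cancer therapy, but a start date known only to the year, or not at all, is left missing, so a response first reached on that therapy can be counted for the study regimen

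*SAP*

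**What the plan says.** SAP section 4.3.1.1 derives BOR from investigator assessments, starting at first treatment and ending at progression, death or a switch of therapy. The part on the last two reads "or the date of initiation of new anti-cancer therapy (Note: This excludes palliative radiotherapy), or death date, whichever is earliest". The therapy cut-off is therefore defined by a date.

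The rule for incomplete dates is in SAP section 6.2.6, in the row headed "New Anti-Cancer Therapy/ Radiotherapy/ Surgical Procedures for Efficacy Evaluation (e.g., response rate, time to event"). Response rate is named there, so the row governs ORR and DCR. It treats start dates in three ways:

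- Day missing only: imputed from the last dosing date or a last assessment of PD where the month matches. Failing that, "Otherwise, a '01' will be used for the day".
- Day and month missing: "If both month and day are missing, no imputation will be applied".
- Nothing recorded: "Completely missing start dates will remain missing, with no imputation applied".

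For missing outcomes, section 4.3.1.2 says "Participants with unknown or missing responses will be treated as non-responders".

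**The concern.** A blank date cannot be the earliest of several dates. If new therapy is recorded but its start date stays missing, the window as written closes only at progression or death, and scans made on the new therapy remain eligible for BOR.

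Extending the window can only keep or improve a best response, so any error favours the study regimen. The handling is also uneven. A date lacking only its day receives a cut-off, while a less complete date receives none. A known year is not used at all: therapy recorded as starting in one year would not exclude a scan made in the next.

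At stake are the ORR and DCR estimates and their exact confidence intervals in a very small cohort.

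**Working it through.** The SAP states no figure that depends on this rule, so there is nothing to reproduce. The check compares the rules and then gives the scale.

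**Step 1: does another rule close the gap?**

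- The missing-response rule in section 4.3.1.2 does not. In this case the response is present and the therapy date is absent.
- The adverse-event and concomitant-medication rows of section 6.2.6 do not apply to the efficacy cut-off. They do show that the SAP is willing to impute a year-only start date: both set it to treatment start or 1 January. The efficacy row does not.
- Section 4.2.3 plans no sensitivity analysis for the primary endpoint, and none is described for ORR or DCR.

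**Step 2: who can be affected?** All of these must hold:

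1. New therapy starts before RECIST 1.1 progression, since progression and death still close the window.
2. Its start date is year-only or missing.
3. Response assessments continue to be recorded afterwards.
4. The qualifying category is first reached after the switch.

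For ORR, the CR or PR must also be confirmed at least 28 days later. DCR is more exposed, because one SD assessment at 56 days or more from baseline is enough. For example, a participant has SD before day 56, stops for toxicity, switches, and shows SD after day 56 on the new therapy. With the window closed at the switch, the early SD alone does not qualify. With it open, the participant counts as disease-controlled.

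**Step 3: size.** Inputs: 10 to 15 participants per combination (section 1.2), at most 15 per dose level (section 5), exact 95% CI (section 4.3.1.2).

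One participant moves the rate by 100/n points: 100/15 = 6.7 and 100/10 = 10.0.

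For x responders out of n, the Clopper-Pearson limits are the 0.025 quantile of Beta(x, n − x + 1) and the 0.975 quantile of Beta(x + 1, n − x), with lower limit 0 when x = 0:

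| x/n | Rate (%) | Exact 95% CI (%) |
|---|---|---|
| 0/15 | 0.0 | 0 to 21.8 |
| 1/15 | 6.7 | 0.2 to 31.9 |
| 2/15 | 13.3 | 1.7 to 40.5 |
| 0/10 | 0.0 | 0 to 30.8 |
| 1/10 | 10.0 | 0.3 to 44.5 |

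One misattributed response at n = 15 would turn 0% into 6.7%, or 6.7% into 13.3%. At n = 10 it would turn 0% into 10%.

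**The case against.** The strongest reply is that the SAP never says the window stays open. It says only that an unknown date is not imputed; the rest is an inference about how a program treats a blank. That is fair as far as it goes. A reader might infer that the SAP deliberately credits responses on later therapy, or that its two sections contradict each other outright. The text supports neither. What stands is that the only stated rule, applied as written, leaves no therapy cut-off. Someone would otherwise have to choose one with the responses in view, in an open-label study with investigator-assessed response.

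The second reply is that the chain of conditions is long and the SAP gives no sign that any such participant exists. This stands, and it limits the size. A reader might also infer that every such participant adds 6.7 points to both rates. That is wrong. Someone with qualifying SD before the switch does not change DCR, and someone with a confirmed response before the switch changes neither.

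The third reply is that the stakes are low. ORR and DCR are secondary and preliminary, Part 1 is about safety, outputs are reduced to support closure, and no test depends on these rates. With "A maximum of 15 participants will be enrolled to each scheduled dose level of ipilimumab in Part 1" and a planned subject-level response listing, an odd case could be found by eye. This also stands, but a listing does not say which cut-off the tabulated rate should use.

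**Conclusion.** The point holds as a gap in a stated rule that can bias ORR or DCR upwards. The effect is at most 6.7 points per affected participant at n = 15 and 10 points at n = 10, and only where the participant had not already qualified.

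The number affected is not in the document. The assumed range of 0 to 1 per cohort includes no effect. At the upper end, 1/15 (0.2 to 31.9%) and 2/15 (1.7 to 40.5%) have heavily overlapping intervals. The document does not support saying that ORR or DCR will be inflated, only that it can be. Since Part 1 is descriptive, no error rate is involved. The change is still worth making because it is cheap and settles the cut-off before the final analysis.

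**What to change.** In section 6.2.6, for the BOR window only, replace the two no-imputation lines for start dates with the following:

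- Query any year-only or missing start date of new anti-cancer therapy before database freeze.
- If it is still year-only, use the later of 1 January of that year and last dosing date + 1.
- If it is wholly missing and new therapy is recorded, use last dosing date + 1.
- List the affected participants, and show ORR and DCR with and without the imputed cut-off.

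The PD + 1 clause of the missing-day rule should not be carried into these lines. Progression already closes the window, and the clause could readmit the very responses at issue. Suppose therapy starts in March with only the year recorded, PR is seen in May and July, and PD follows in November. A cut-off on the day after PD would count both PRs.

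The cost is a few lines of text and a small derivation change. The drawback is a possible error the other way: a genuine response confirmed after the last dose, but before the true start of new therapy, may lose its confirmation scan and with it the same 6.7 or 10 points. That error is conservative, and the listing and the paired estimates make it visible. Neither imputation recovers the true date, which is why the query comes first.
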